Study Protocol

This is the translated version of the Study Protocol (Version 4) written in Japanese

Study title:	Phase-3 clinical study of duloxetine hydrochloride in children and adolescent patients with depressive disorder: An open-label extension study
Study No.:	1702A3632
Development phase:	3
Product No.:	LY248686
Sponsor:	Shionogi & Co., Ltd. (Head Office) [name]
Contact information for the sponsor:	[REDACTED] [REDACTED] [REDACTED] [REDACTED] [REDACTED]
Emergency contact:	[REDACTED] [REDACTED] [REDACTED] [REDACTED] [REDACTED]

Preparation dates

First version (Version 1):	September 25, 2017
Version 2	October 20, 2017
Version 3	February 23, 2018
Version 4	August 8, 2018

This protocol contains confidential information belonging to Shionogi & Co., Ltd.

The information in this protocol should not be disclosed to a third party without permission from Shionogi & Co., Ltd. Reproduction of this protocol by photocopying, etc., is also prohibited.

Overview of the study

Study title: Phase-3 clinical study of duloxetine hydrochloride in children and adolescent patients with depressive disorder: An open-label extension study

Study No.: 1702A3632

Development phase: 3

Primary objective: To evaluate the long-term safety of duloxetine in children and adolescent patients with depressive disorder.

Secondary objectives:

- To evaluate the long-term efficacy of duloxetine in children and adolescent patients with depressive disorder.
- To evaluate the pharmacokinetics of duloxetine in Japanese children and adolescent patients with depressive disorder.
 - To compare the plasma duloxetine concentrations at steady state obtained at 5 time points (including at least one predose level [trough]) in children and adolescent patients with depressive disorder with those of adult patients with depressive disorder.
 - To examine the potential factors that affect the pharmacokinetic properties of duloxetine (e.g., age, body weight, and sex) and their effects in the population pharmacokinetics analysis.
- To evaluate the relationship between duloxetine exposure at steady state and Children's Depression Rating Scale-Revised (CDRS-R) total score, one of the efficacy endpoints.

Study design: This study is a multicenter, open-label, uncontrolled, long-term treatment study in children and adolescent patients with depressive disorder. This study will include a total of 135 patients; consecutive subjects who have completed the preceding study "Phase-3 clinical study of duloxetine hydrochloride in children and adolescent patients with depressive disorder: Superiority study versus placebo" (Study No.: 1701A3631) then wish to continue the study treatment will be enrolled, as well as additional subjects who have child and adolescent depressive disorder, with a target of 100 subjects completing a 1-year treatment.
This study will consist of the following four periods (a total of 53 to 56 weeks): screening period (1 to 3 weeks), treatment period (50 weeks), tapering period (1 to 2 weeks), and follow-up period (1 week). Note that consecutive subjects will undergo three periods (a total of 52 to 53 weeks), excluding the screening period. New subjects whose eligibility has been confirmed after obtaining informed consent will be pre-registered (Visit 1), and, after completion of the 1- to 3-week screening period, their eligibility will be confirmed again and they will be registered (Visit 2).

Consecutive subjects will give consent for this study before completing the observation at Visit 9 in the preceding study, and, after completing the observation at Visit 9 in the preceding study and the eligibility of this study is confirmed, be enrolled in this study from Visit 2 (registration).

After registration, the study drug will be administered orally, once daily after breakfast.

Study subjects: The subjects must meet the following criteria: (i) aged ≥ 9 to <18 at the time of obtaining consent and assent (consecutive subjects are allowed to be enrolled if they are aged ≥ 9 to <18 in the preceding study); (ii) diagnosed as having depression or persistent depressive disorder as defined in the Diagnostic and Statistical Manual of Mental Disorders, version 5 (DSM-5), with onset at the age of ≥ 7 ; and (iii) fully meeting the criteria for a depressive episode. The Mini-International Neuropsychiatric Interview for Children and Adolescents (MINI-KID; version 7.0.2) will be used for diagnosis on the basis of DSM-5.

Inclusion/exclusion criteria:	Subjects must meet all the following criteria:	Consecutive subjects	New subjects
	Inclusion criteria		
1) Have completed 7-week treatment in the preceding study and wish to continue treatment with duloxetine.		X	
2) Have been diagnosed with depression or persistent depressive disorder, as defined in DSM-5, and fully meet the criteria for a depressive episode. MINI-KID (version 7.0.2) should be used for diagnosis of depression.			X
3) Are aged ≥ 9 to <18 at the time of obtaining consent and assent, and must have been ≥ 7 at the initial onset of depression episode. Are male or female and are hospitalized or out-patients.			X
4) Have a legal representative capable of providing written informed consent for this study. In addition, for patients aged ≥ 13 , a written, informed assent must also be obtained from the patient him/herself. For patients aged ≥ 9 to <13 , a written, informed assent should also be obtained from the patient him/herself if possible.		X	X
5) For post-menarchic females, a pregnancy test result must be negative at Visit 1 (or Visit 2 for consecutive subjects). In addition, the patient must agree to use one		X	X

of the following contraceptive methods from Visit 1 (or Visit 2 for consecutive subjects) until 1 month after the final administration. However, this requirement does not apply to females for whom it can be confirmed in writing that 6 weeks or more has passed since bilateral ovariectomy.
 
Estrogen- and progesterone-containing, combined-hormonal contraceptive agents with ovulation-suppressing effects (administered orally, intravaginally, subcutaneously, etc.), progesterone-containing hormonal contraceptive agents (administered orally, intravenously, by implantation, etc.), intrauterine device, intrauterine system, bilateral tubal ligation, male partner's vasectomy, or sexual abstinence.
		

6) The principal investigator or sub-investigator judges that the subject's legal representative can ensure that the subject him/herself will comply with all hospital visits, tests, and other procedures stipulated in this protocol. In addition, the principal investigator or sub-investigator judges that the subject him/herself will be able to comply with all the hospital visits, tests, and other procedures stipulated in this protocol.
		X

7) The principal investigator or sub-investigator judges that the subject's legal representative has sufficient comprehension and cognitive ability to communicate as appropriate with the principal investigator or sub-investigator, and other persons involved with the study. In addition, the principal investigator or sub-investigator confirms that the subject him/herself has a cognitive level appropriate to his/her age, and judges that he/she has sufficient comprehension and cognitive ability to communicate as appropriate with the principal investigator or sub-investigator, and other persons involved with the study.
		X

8) Have ability to swallow the capsules without opening, crushing, dissolving, or breaking them. In addition,
		X

he/she can take up to three capsules per day.		
---	--	--

Patients who meet any of the following criteria will be excluded:

Exclusion criteria	Consecutive subjects	New subjects
1) Judged by the principal investigator or sub-investigator to have complications diagnosed as belonging to one or more of the following categories in DSM-5, or to have a history of such disorders: 
• Neurodevelopmental disorders• Schizophrenia-spectrum disorder or other psychotic disorders• Bipolar or related disorders• Trauma and stressor-related disorders• Disruptive, impulse-control, and conduct disorders	X	X
2) Judged by the principal investigator or sub-investigator to have complications diagnosed as belonging to one or more of the following categories in DSM-5: 
• Obsessive-compulsive disorder or related disorders• Anorexia nervosa, bulimia nervosa, or binge-eating disorder• Sleep-wake disorders• Neurocognitive disorders• Disruptive mood dysregulation disorder	X	X
3) Judged by the principal investigator or sub-investigator to have a personality disorder.	X	X
4) Treatment with two or more antidepressants has previously been tried, and, despite treatment of a single depressive episode with the optimal clinical dose for 4 weeks or more, there has been no response. Alternatively, the depressive episode has been treated previously or is currently being treated with duloxetine, but without response.		X
5) The principal investigator or sub-investigator judges	X	X

that systematic psychotherapy must be initiated between Visits 1 and 18.		
6) One or more of the patient's parents and/or siblings has been diagnosed with bipolar disorder.	X	X
7) A history of epileptic or other convulsive attacks. However, patients with a history of febrile convulsions can be enrolled.	X	X
8) Administered electroconvulsive therapy within 1 year before Visit 1.		X
9) Uncontrolled diabetes or collagen disease.		X
10) Have initiated, changed or discontinued hormonal therapy within 3 months before Visit 1. Patients with thyroid dysfunction are excluded. But patients can be enrolled if they (i) have undergone thyroid hormone supplementation at a consistent dose for at least 3 months as of Visit 1; (ii) show medically appropriate thyroid hormone (TSH, FT ₃ , FT ₄) concentrations; and (iii) have clinically normal thyroid function.		X
11) Currently have or have a history of malignant tumors/cancer.	X	X
12) For new subjects, either (i) suicidal ideation and/or suicidal attempt within 1 year before Visit 1; or (ii) at Visits 1 and 2 (or Visit 2 for consecutive subjects), answer "Yes" to questions 4 and/or 5 about suicidal ideation, and/or any of the questions about suicidal behaviors (except those about non-suicidal self-injurious behavior), on the Columbia suicide severity rating scale (C-SSRS).	X	X
13) Body weight below 20 kg at Visit 2.	X	X
14) Serious ^{*1} or medically unstable ^{*2} disease (cardiovascular disease, hepatic disease, respiratory disease, hematologic disease, endocrine disease, peripheral vascular disorder, neuropsychiatric disease, renal disease), or clinically problematic abnormal laboratory test results or abnormal electrocardiography (ECG) findings ^{*3} .	X	X

*1: Grade 3 in "Concerning classification criteria for

seriousness of adverse drug reactions to pharmaceutical products, etc.” (Drug Safety Notification no. 80; June 29, 1992).
 
*2: Judged by the principal investigator or sub-investigator to have the potential to disrupt study participation, or to necessitate hospitalization during the study period.
 
*3: Judged by the principal investigator or sub-investigator to suggest serious medical problems, or to necessitate aggressive therapy.
		

15) Meeting one or more of the following criteria:
 
 • At Visit 2, latest ALT or AST of 100 U/L or higher, or latest total bilirubin of 1.6 mg/dL or higher. • Latest serum creatinine level of 2.0 mg/dL or higher at Visit 2. Or have severe renal impairment, history of renal transplantation, and/or currently undergoing renal dialysis. 	X	X

16) Glaucoma, elevated intraocular pressure, and/or prostatic hypertrophy or other types of dysuria.
	X	X

17) Depression or depressive state due to organic brain disorder.
	X	X

18) Hemorrhagic tendency or hemorrhagic diathesis.
	X	X

19) Treatment with monoamine oxidase (MAO) inhibitor within 14 days before Visit 2, and/or potential for MAO inhibitor treatment during the study period or within 5 days after completion of study drug administration.
	X	X

20) Hypersensitivity to duloxetine or inactive ingredients of duloxetine formulation.
	X	X

21) Allergic to two or more drugs, or a history of serious allergic reactions to one or more drugs.
	X	X

22) Judged by the principal investigator or sub-investigator to have the complication of substance-related and/or addictive disorders, as defined in DSM-5, or a history of such disorders. However, patients with caffeine-related disorder can be enrolled.
		X

23) One or more substances of abuse (phencyclidines,
		X

benzodiazepines, cocaine-type drugs, stimulants, cannabis, opioids, barbiturates, tricyclic antidepressants, etc.) detected by urinary drug screening at Visit 2.		
24) Intension to travel overseas between Visit 1 (or Visit 2 for consecutive subjects) and Visit 6.	X	X
25) Pregnant* or possibly pregnant, breastfeeding, hoping to become pregnant during the study period. Or recently given birth. * Pregnancy: Pregnancy tests (blood or urine human chorionic gonadotropin) will be performed in all post-menarche females.	X	X
26) Previously administered the study drug during participation in this study, or during participation in a different clinical study on duloxetine.		X
27) Have received another study drug within 30 days before Visit 1 or are currently receiving it.		X
28) Participation judged to be inappropriate for any other reason by the principal investigator or sub-investigator.	X	X

Study drug dosage and administration method:
All subjects will receive 1 to 3 oral capsules of duloxetine 20 mg once daily after breakfast from the day after the registration (Visit 2).
During the treatment period, subjects will receive duloxetine 20 mg/day for one week then 40 mg/day for one week, and subsequently receive 40 mg/day or 60 mg/day for 48 weeks depending on the symptoms.
During the tapering period, the subjects whose duloxetine dose at discontinuation or completion of the treatment period is 60 mg/day will receive 40 mg/day for one week then 20 mg/day for one week. The subjects whose duloxetine dose at discontinuation or completion of the treatment period is 40 mg/day will receive 20 mg/day for one week.

Administration period:
51 or 52 weeks (50-week treatment period and 1- to 2-week tapering period)

Prohibited drugs and therapies:
Use of the below drugs, or over-the-counter drugs with equivalent effects, is prohibited from Visit 1 (or after completing the observation period at the completion of the tapering period in the preceding study for consecutive subjects) through to Visit 18 (completion of the tapering period):
Prohibited drugs that may affect therapeutic evaluation:
1) Antidepressants

- 2) Anxiolytics
- 3) Soporific agents, other than the “Permitted soporific agents” in Section 6.2.2
- 4) Antipsychotics
- 5) Antiparkinsonian agents
- 6) Anticonvulsants
- 7) Mood-stabilizers (lithium carbonate, carbamazepine, sodium valproate)
- 8) Psychostimulants
- 9) Adrenal corticosteroids (excluding topical agents, such as ear drops, nose drops, eye drops, topical skin formulations, and inhaled formulations).
- 10) Interferon formulations
- 11) Any of the following drugs, which might affect the metabolic/agonistic activities of serotonin or noradrenaline:
 - Cyproheptadine hydrochloride (Periactin®, etc.)
 - Dimetotiazine mesilate (Migristene®)
 - Ifenprodil tartrate (Cerocral®, etc.)
 - 5-HT₃ inhibitors (Zofran®, etc.)
 - 5-HT₄ stimulants (Gasmotin®, etc.)
 - 5-HT_{1B/1D} receptor agonists (Imigran®, etc.)
 - Adrenergic agents (Noradrenaline®, etc.)
- 12) St. John’s wort
- 13) Chinese herbal medicines administered to treat central nervous conditions such as insomnia, neurosis or anxiety.
- 14) Other agents judged to act on the central nervous system, and thus affect therapeutic evaluation.

Prohibited drugs that present safety-related problems:

- 1) MAO inhibitors** (FP®, Azilect®, etc.)

**Administration of these is contraindicated from 14 days before Visit 2 (or after completing the observation period at the completion of the tapering period in the preceding study for consecutive subjects) until 5 days after completion of study drug administration.

- 2) Other investigational drugs

Unless specifically stated otherwise, use of the following treatments is contraindicated from Visit 1 (or after completing the observation period at the completion of the tapering period in the preceding study for consecutive subjects) through to Visit 18 (completion of the tapering period):

- 1) Electroconvulsive therapy
- 2) Bright-light therapy, i.e. therapy using irradiation devices approved as medical devices.
- 3) Systematic psychotherapy, such as systematically organized cognitive therapy, cognitive behavioral therapy, and interpersonal psychotherapy. For new subjects, this study will use educational tools, consistently in all institutions, for the psycho-education of subjects and guardians.
- 4) Exercise therapy
- 5) Hormone therapy is contraindicated. However, in accordance with exclusion criterion 10, treatment can be continued at the same dose in thyroid dysfunction patients who meet the following three criteria: (i) having undergone thyroid hormone supplementation for at least 3 months as of Visit 1 (or Visit 2 for consecutive subjects); (ii) showing medically appropriate concentrations of thyroid hormones (TSH, FT₃ and FT₄); and (iii) having attained a clinically normal state of thyroid function.

Efficacy endpoints:	CDRS-R, Clinical Global Impression of Severity (CGI-S)
Pharmacokinetic endpoint:	Plasma duloxetine concentrations
Safety endpoints:	Adverse events, adverse drug reactions, C-SSRS score, laboratory test results, blood pressure, pulse rate, body weight, ECG
Statistical methods:	The summary statistics will be calculated for the observed efficacy endpoints (CDRS-R total score and CGI-S) and their changes from baseline at each time-point after study drug administration. In principle, the baseline for each endpoint is defined as the subject's initiation of this study (Visit 2).
Study period:	Study period for each subject: Up to 56 weeks (consisting of a 1- to 3-week Screening period, a 50-week treatment period, a 1- to 2-week tapering period, and a 1-week follow-up period). Scheduled study period: From November 2017 to March 2021.
Date of preparation of the first version:	September 25, 2017
Date of preparation of the latest version:	August 8, 2018 (Version 4):

Table of contents

Overview of the study	2
Table of contents	11
List of Tables	14
List of Figures	14
List of abbreviations and definitions of terms	15
1. Background information	16
2. Study objectives	19
2.1 Primary objective	19
2.2 Secondary objectives	19
3. Study plan	20

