- Tapering period: In order to minimize the occurrence of adverse events due to discontinuation of administration, a 1- to 2-week tapering period is set for subjects who complete the treatment period, or who withdraw from it during the second week or later. Subjects whose duloxetine dose at discontinuation or completion of the treatment period is 60 mg/day will receive 40 mg/day for one week then 20 mg/day for one week. If the dose at discontinuation or completion is 40 mg/day, 20 mg/day will be administered for one week.
- Follow-up period: No study drugs will be administered during the 1-week follow-up period. This period is set to enable evaluation of any adverse events during the week after completion of study drug administration, irrespective of whether or not the dose was tapered. If administration is discontinued during the treatment period, and there is then no administration during the tapering period, a 1-week follow-up period will be set after administration discontinuation.

The study design is shown in Fig. 3-1. The study schedule is shown in Appendix 1.

Fig. 3-1. Schematic diagram of study schedule

Until 50 weeks after treatment initiation, the dose may be increased to 40 mg/day or 60 mg/day as appropriate, depending on the symptoms.

Consecutive subjects will start this study from Visit 2 after completing Visit 9 in the preceding study.

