7.5 Efficacy evaluation

7.5.1 Children's Depression Rating Scale-Revised (CDRS-R)

At Visits 1 (or Visit 2 for consecutive subjects) to 17 (or at discontinuation of treatment), the severity of symptoms for the below 17 items will be judged using CDRS-R (Table 7-1). The date and results of evaluation will be recorded in the CRF. At discontinuation of treatment, evaluation will be performed if possible, and recorded in the CRF.

Table 7-1. Children's Depression Rating Scale-Revised

Endpoints	Score range	Endpoints	Score range
1. Impaired Schoolwork	1 to 7	11. Depressed Feelings	1 to 7
2. Difficulty Having Fun	1 to 7	12. Morbid Ideation	1 to 7
3. Social Withdrawal	1 to 7	13. Suicidal Ideation	1 to 7
4. Sleep Disturbance	1 to 5	14. Excessive Weeping	1 to 7
5. Appetite Disturbance	1 to 5	15. Depressed Facial Affect	1 to 7
6. Excessive Fatigue	1 to 7	16. Listless Speech	1 to 5
7. Physical Complaints	1 to 7	17. Hypoactivity	1 to 7
8. Irritability	1 to 7		
9. Excessive Guilt	1 to 7		
10. Low Self-Esteem	1 to 7	Total	17 to 113

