7.5.2 Clinical Global Impression of Severity (CGI-S)

At Visits 1 (or Visit 2 for consecutive subjects) to 17 (or at discontinuation of treatment), the principal investigator or sub-investigator will evaluate the disease severity in terms of the below grades 1 to 7. The date and results of evaluation will be recorded in the CRF. At discontinuation of treatment, evaluation will be performed if possible, and recorded in the CRF.

1. Normal / no disease	2. Bordering on disease	3. Mild disease	4. Moderate disease
5. Marked disease	6. Severe disease	7. Extremely severe disease	

[figure not shown]

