7.7.7 Evaluation of adverse events

7.7.7.1 Evaluation methods for adverse events

An adverse event is any unfavorable medical event suffered by someone administered a pharmaceutical product (including a study drug) and does not necessarily have a causal relationship with the relevant pharmaceutical product. In other words, an adverse event is any unfavorable and/or unexpected sign (including abnormal laboratory test result), symptom, or disease associated with the administration of a drug, irrespective of any causal relationship with that drug. Surgery that was already planned is not considered to be an adverse event, unless it leads to exacerbation of an existing disease, and is therefore not considered to be a serious adverse event even if it necessitates hospitalization. However, if an additional surgery is performed in connection with the planned surgery, this is taken to be an adverse event, and to be a serious adverse event if prolongation of hospitalization is required, or if any other criterion for being a serious adverse event is met. Hospitalization or prolongation of hospitalization for reasons other than adverse events is not considered to constitute a serious adverse event.

The presence or absence of an adverse event will be confirmed on the basis of the subject's spontaneous complaint, non-inductive questions, examination, C-SSRS, blood pressure, pulse rate, body weight, and ECG or laboratory test results. Adverse events include new onset of an event, increase in the severity or frequency of an event since administration initiation, and diagnostic abnormality, including abnormal laboratory test results. A symptom recorded as a medical history at study initiation will be handled as an adverse event only when symptoms are aggravated. In addition, loss of efficacy, and changes in the primary disease (depression) or scores for any of the CDRS-R items, will not be handled as adverse events in this study, unless judged to be serious adverse events.

The principal investigator or sub-investigator will evaluate adverse events. The principal investigator or sub-investigator will carefully investigate each adverse event, and record in the CRF the date of onset, time of onset, date of cessation (if the outcome is recovery or death), severity, seriousness (including the reason for judging seriousness), causal relationship with the study drug, actions taken for the adverse event, and outcome of the adverse event.

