6.3 Assessments, observations and tests: Permitted timing and handling in statistical analyses

In principle, data obtained at the time-points shown in the case report forms, and collected in accordance with the performance schedule shown in the study protocol, will be used for the statistical analysis. In the case of data reported at the discontinuation visit, the time-points for use in analyses will be determined on the basis of the permitted ranges in the performance schedule. If there is duplication by data obtained at the scheduled visits and data obtained at the discontinuation tests, the data obtained closest to the scheduled date will be used. If this does not eliminate duplication, data from the scheduled visit will be used. Unscheduled visits will not be included in the time-points for analysis. For the permitted ranges for the observation, test, and evaluation time-points shown in the study protocol, refer to Appendix 2.

For the final evaluation, data obtained at weeks 51 to 52 or at discontinuation of the treatment/tapering period will be used, except for CDRS-R and CGI-S scores, for which those obtained at week 50 or at discontinuation of the treatment period are used. However, if none of the above data are available, the latest data among reported data collected at scheduled visits are used for the final evaluation.

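### Non-serious worsening of depression during the taper or the drug-free week is rated on no depression scale and is not an adverse event, so the taper-period safety table cannot show it

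*Protocol*

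**What the plan says.** The Overview and protocol section 3.1 set four periods: "screening period (1 to 3 weeks), treatment period (50 weeks), tapering period (1 to 2 weeks), and follow-up period (1 week". Visit 18 closes the taper and Visit 19 the follow-up. Section 3.1 says of the follow-up: "This period is set to enable evaluation of any adverse events during the week after completion of study drug administration".

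Depression severity is rated on two scales, both ending at Visit 17. Section 7.5.2 has CGI-S rated from Visit 1 (Visit 2 for consecutive subjects) "to 17 (or at discontinuation of treatment), the principal investigator or sub-investigator will evaluate the disease severity". Section 7.5.1 gives the same visits for CDRS-R, where "the severity of symptoms for the below 17 items will be judged using CDRS-R (Table 7-1". The schedule tables in Appendix 1 of the protocol and of the SAP show neither scale at Visit 18 or 19. SAP section 6.3 takes the final evaluation of other measures from weeks 51 to 52 or discontinuation, "except for CDRS-R and CGI-S scores, for which those obtained at week 50 or at discontinuation of the treatment period are used".

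On adverse events, protocol section 7.7.7.1 states that "loss of efficacy, and changes in the primary disease (depression) or scores for any of the CDRS-R items, will not be handled as adverse events", with an exception for those judged serious. SAP section 10.1, item 6, plans a table of adverse events occurring during the taper.

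**The concern.** The primary objective is long-term safety, and how subjects fare as the drug is withdrawn after up to a year bears on it. A worsening of depression could be captured as a score on a depression scale or as an adverse event. The visit schedule removes the first route after Visit 17, and the adverse-event definition removes the second for anything not judged serious.

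A subject whose CGI-S would have gone from 2 to 5 during the taper, without meeting a seriousness criterion, has no score and no adverse event. The taper table in SAP 10.1 will still list other events that arise on discontinuation. A reader of that table cannot tell whether depression stayed stable or was simply not rated.

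**Working it through.** **1. What is collected at the end of the study**

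| Item | Visit 17 (week 50) | Visit 18 (end of taper) | Visit 19 (follow-up) | Source (protocol) |
|---|---|---|---|---|
| CDRS-R | yes | no | no | 7.5.1, Appendix 1 |
| CGI-S | yes | no | no | 7.5.2, Appendix 1 |
| C-SSRS (suicidality only) | yes | yes | not called for | 7.7.2 |
| Physical examination, looking for adverse events | yes | yes | yes | 7.7.1 |
| Adverse events, excluding non-serious change in depression | yes | yes | to 7 days after last dose | 7.7.7.1, 7.7.7.2 |
| Concomitant treatments with reasons for use | yes | yes | yes | 6.2 |

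**2. What each remaining trace can show**

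- Serious adverse events (7.7.7.1, 7.7.7.2, 7.7.7.8) capture serious worsening only.
- C-SSRS covers suicidal ideation and behavior, not depression severity.
- Taper-withdrawal reasons (SAP 7.1; aggravation of the primary disease is a listed reason in protocol 4.5) miss a subject who worsens but finishes the taper, or who worsens in the drug-free week.
- Concomitant treatments leave a record when a subject is re-treated, but SAP 8.2 tabulates them over the whole study period, not after Visit 17.

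None of these gives a severity or a rate of worsening.

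**3. Length of the unrated time (protocol Table 7-3 and Appendix 1)**

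The stated totals reproduce: 1 + 50 + 1 + 1 = 53 weeks and 3 + 50 + 2 + 1 = 56 weeks. The last scheduled rating is on day 350.

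- Last dose 40 mg/day: 7 days of taper + 7 of follow-up = 14 days (day 350 to 364).
- Last dose 60 mg/day: 14 + 7 = 21 days (day 350 to 371, as in Appendix 1).

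The windows (Visit 17 ±3 days; discontinuation visit up to 3 days after the last treatment-period dose) could place a last rating a few days after the full dose ends. That is not a planned post-withdrawal rating.

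**4. How many subjects**

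Plan's figure: 100 / (1 − 0.25) = 133.3, rounded up to 134; the stated 135 agrees closely. Expected completers: 135 × 0.75 = 101.25, about 101. Unrated time: 101 × 2 = 202 to 101 × 3 = 303 subject-weeks. Early withdrawals who taper would add to this, and completers whose taper is omitted would add less.

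**5. What a Visit 18 rating could estimate**

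The documents give no rate of worsening on withdrawal. The counts below are assumptions that show precision only, using exact (Clopper-Pearson) 95% intervals with n = 101. For zero events the upper limit is 1 − 0.025^(1/101) = 0.036.

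| Worsened / 101 | Rate | 95% CI |
|---|---|---|
| 0 | 0% | 0 to 3.6% |
| 5 | 5.0% | 1.6 to 11.2% |
| 10 | 9.9% | 4.9 to 17.5% |
| 15 | 14.9% | 8.6 to 23.3% |

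With CGI-S at Visit 18, the nominal unrated time falls from 14 or 21 days to the 7 days of follow-up.

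**The case against.** The strongest case against is that this is a deliberate and consistent design. Protocol and SAP agree that the last depression rating is at week 50 or treatment discontinuation. No objective names relapse on withdrawal. Section 3.1 sets the taper to reduce adverse events from stopping, and the follow-up to look for adverse events; neither was set up to measure relapse. All of that stands, and it makes this a gap in measurement rather than an error.

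A reader might infer that a return of depression leaves no record at all. The documents do not support that, because the traces in step 2 of the working exist. The gap is limited to non-serious worsening, and to the absence of a severity or a rate.

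A reader might also take the background's remark that pediatric depression recurs easily as a sign of many missed cases. The survey of 65 patients cited there reports 40% recurrence within 2 years after recovery. Under a constant hazard (an assumption), that is 1 − 0.6^(2/104) = 1.0% over 2 weeks and 1 − 0.6^(3/104) = 1.5% over 3 weeks, or roughly 1 to 1.5 of 101 subjects. The figure is not specific to drug withdrawal, so it neither establishes nor rules out a larger problem.

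Finally, ratings at Visit 19 would be hard to interpret. Contact may be by telephone (Appendix 1, note j), so attendance is selective. The prohibitions on antidepressants and other therapies end at Visit 18 (section 6.2.1), so untreated and newly re-treated subjects would be mixed. This stands, and it is why the fix rests on Visit 18.

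**Conclusion.** The gap is real and limited. From Visit 17 or treatment discontinuation onward, a non-serious worsening of depression is neither rated on a depression scale nor counted as an adverse event, and the taper-period adverse-event table cannot show it. For completers this covers 14 or 21 nominal days, about 202 to 303 subject-weeks if the planned 25% dropout holds and all completers taper. How many subjects worsen cannot be estimated from the documents. Closing the gap at Visit 18 is a cheap improvement to a long-term safety study, not the repair of a contradiction.

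**What to change.** - **Schedule.** In protocol section 7.5.2 and Appendix 1, and in SAP Appendix 1, add CGI-S at Visit 18 or at discontinuation of the tapering period.
- **Efficacy unchanged.** Keep week 50 or treatment discontinuation as the final efficacy evaluation. SAP 6.3 falls back on the latest scheduled-visit value when the final one is missing; state that for CGI-S this fallback uses treatment-period visits only, so that a Visit 18 rating cannot enter the efficacy result.
- **Analysis.** In SAP section 10, for subjects who enter the taper, report the number and percentage whose CGI-S at Visit 18 is worse than their last treatment-period rating by at least 1 grade and by at least 2 grades, with Clopper-Pearson 95% intervals. State how many taper subjects lack the rating.
- **Interpretation.** Label the result descriptive. Without a control it cannot separate relapse from discontinuation symptoms, and a one-grade change is not by itself a relapse.
- **Visit 19.** Any CGI-S there should be optional and listed only, with treatments started after Visit 18 flagged.

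The cost is a protocol amendment, one CRF field and one 7-point rating by an investigator who already examines the subject at Visit 18. No visit is added. The drug-free week stays without a systematic rating, which the study report should say.
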